#### ***10.3.4 Demographic and Baseline Characteristics***

Demographic and Baseline characteristics (age, gender, race, ethnicity, body mass index) will be summarized by treatment group across cohorts and by treatment group pooled across all cohorts for each analysis set separately.

#### **10.4 Statistical Analysis Plan (SAP)**

The SAP will be developed and finalized prior to the database lock and unblinding of treatment assignment. This plan will confirm the analysis sets used in the analysis, outline all data handling conventions, and specify all statistical methods to be used for all safety and efficacy analyses. The SAP will supersede the protocol with respect to analyses specified, although the primary analysis will remain the same. It is only anticipated that additional analyses may be desired to be pre-specified in the SAP.

---

## **11 DATA QUALITY ASSURANCE**

Accurate, consistent, and reliable data will be ensured through the use of standard practices and procedures. These are described in the following sections.

### **11.1 Data Handling**

Data will be entered into an electronic database and reviewed by the Clinical Research Associate (CRA) remotely. All corrections or changes made to any study data must be appropriately tracked in an audit trail in the eCRF system. The eCRFs will be considered complete when all missing, incorrect, and/or inconsistent data have been accounted for.

### **11.2 Computer Systems**

Data will be processed using a validated computer system conforming to regulatory requirements.

### **11.3 Data Entry**

Data must be recorded using the eCRF system as the study is in progress. All study site personnel must log into the system using their secure user name and password in order to enter, review, or correct study data. These procedures must comply with 21 CFR Part 11 and other appropriate international regulations. All passwords will be strictly confidential.

### **11.4 Medical Information Coding**

The latest version of the WHO Drug Dictionary and MedDRA will be used for coding of concomitant medications and AEs.

### **11.5 Data Validation**

Validation checks programmed within the eCRF system, as well as supplemental validation performed via review of the downloaded data, will be applied to the data in order to ensure accurate, consistent, and reliable data. Data identified as erroneous, or data that are missing, will be referred to the investigative site for resolution through data queries.

The eCRFs must be reviewed and electronically signed by the Investigator who signed the protocol.

### **11.6 Study Monitoring Requirements**

It is the responsibility of the Investigator to ensure that the study is conducted in accordance with the protocol, Declaration of Helsinki, ICH GCP guidelines, and applicable regulatory requirements, and that valid data are entered into the eCRFs.

The Investigator will permit the Sponsor or their designee to monitor the study as frequently as deemed necessary to determine that data recording and protocol adherence

---

are satisfactory. Monitoring will include review of the eCRFs for completeness and clarity, cross-checking with source documents, and clarification of administrative matters. The review of medical records will be performed in a manner to ensure that patient confidentiality is maintained. All monitoring activities will be reported and archived. In addition, monitoring visits will be documented by CRA signature and date on the study-specific monitoring log and the completion of a detailed monitoring report.

The CRA will ensure that the investigation is conducted according to protocol design and regulatory requirements by frequent communications with the investigational site (monitoring visits, letter, telephone, email, and fax).

All unused study drug and other study materials are to be returned to the Sponsor or designee after the clinical phase of the study has been completed.

Regulatory authorities, the IRB, and/or the Sponsor's clinical quality assurance group may request access to all source documents, eCRFs, and other study documentation for on-site audit or inspection. Direct access to these documents must be guaranteed by the Investigator, who must provide support at all times for these activities.

### **11.7 Source Document and Case Report Form Completion**

Source data is defined as all information in original records and certified copies of original records of clinical findings, observations, or other activities in a clinical study necessary for the evaluation and reconstruction of the clinical study. Source data are contained in source documents (ie, original records or certified copies). Source documents and the eCRFs will be completed for each study patient. It is the Investigator's responsibility to ensure the accuracy, completeness, and timeliness of the data reported in the patient's source document/eCRF. The source document/eCRF should indicate the patient's participation in the study and should document the dates and details of study procedures, AEs, and patient status.

The Investigator, or designated representative, should complete the source document/eCRF as soon as possible after information is collected, preferably on the same day that a study patient is seen for an examination, treatment, or any other study procedure. Any outstanding entries must be completed immediately after the final examination. An explanation should be given for all missing data.

The Investigator must sign and date the Investigator's Statement at the end of the source document/eCRF to endorse the recorded data.

The Investigator will retain all completed source documents. A site-specific eCRF archive and audit trail will be provided at the close of the study to each Investigator. The Sponsor or designee will retain the eCRF archive and audit trail for all investigative sites.

---

## **11.8 Record Retention**

Records of patients, source documents, monitoring visit logs, eCRFs, inventories of study product, regulatory documents, and other correspondence pertaining to the study must be kept in the appropriate study files at the site. The Investigator will maintain all study records according to ICH GCP and applicable regulatory requirements. Records will be retained for at least 2 years after the last marketing application approval or 2 years after formal discontinuation of the clinical development of the investigational product or according to applicable regulatory requirements. If the Investigator withdraws from the responsibility of keeping the study records, custody must be transferred to a person willing to accept the responsibility. The Sponsor must be notified in writing if a custodial change occurs.

---

## **12 ETHICS**

### **12.1 Good Clinical Practice**

The study will be conducted in accordance with the protocol, GCP, the relevant ICH guidelines, the applicable regulatory requirements, and the ethical principles that have their origins in the Declaration of Helsinki. As required by US FDA (21 CFR 56) and the Declaration of Helsinki, the study protocol, amendments, and informed consent form will be reviewed and approved, according to 21 CFR Parts 50 and 56 (or similar local requirements, such as ICH E6, for ex-US sites), respectively, by each study center's IRB or EC.

### **12.2 Institutional Review Board**

The IRB will review all appropriate study documentation in order to safeguard the rights, safety, and wellbeing of patients. Federal/local regulations and ICH GCP guidelines require that approval be obtained from an IRB prior to participation of patients in research studies. The study will only be conducted at sites where IRB approval has been obtained. The protocol, Investigator's Brochure, informed consent form, advertisements (if applicable), written information given to the patients, safety updates, annual progress reports, and any revisions to these documents will be provided to the IRB by the Investigator.

No study drug will be released to the site for dosing until written IRB authorization has been received by the Sponsor.

### **12.3 Patient Information and Consent**

The informed consent form and any changes to the informed consent form made during the course of the study must be agreed to by the Sponsor or their designee and the IRB/EC prior to its use and must be in compliance with FDA Regulations in 21 CFR Part 50, Department of Health & Human Service in 45 CFR Part 46 (if applicable), ICH GCP guidelines, local regulatory requirements, and legal requirements.

The Investigator must ensure that each study patient or proxy is fully informed about the nature and objectives of the study and possible risks associated with participation and must ensure that the patient has been informed of his/her rights to privacy. The Investigator will obtain written informed consent from each patient or the patient's legally authorized representative before any study-specific activity is performed and will document in the source documentation that consent was obtained prior to enrollment in the study. The original signed copy of the informed consent form must be maintained by the Investigator and is subject to inspection by the Sponsor, their representatives, auditors, the IRB, and/or regulatory agencies. A copy of the signed informed consent form will be given to the study patient or proxy. Whenever possible, patients who participate based on proxy consent will be re-consented once deemed capable by the Investigator of providing consent on their own.

---

If significant new findings are developed during the course of research which may affect the willingness of patients to continue study participation, the Sponsor will notify each Investigator of the findings via letter or telephone.

#### **12.4 Patient Confidentiality**

In order to maintain patient privacy, all eCRFs, study drug accountability records, study reports and communications will identify the patient by initials and the assigned patient number. The Investigator will grant monitor(s) and auditor(s) from the Sponsor or its designee and regulatory authority(ies) access to the patient's original medical records for verification of data gathered on the eCRFs and to audit the data collection process. The patient's confidentiality will be maintained and will not be made publicly available to the extent permitted by the applicable laws and regulations.

#### **12.5 Protocol Compliance**

The Investigator will conduct the study in compliance with the protocol provided by the Sponsor, the approval/favorable opinion of the IRB and the appropriate regulatory authority(ies). Modifications to the protocol should not be made without agreement of both the Investigator and the Sponsor. Changes to the protocol will require written IRB approval/favorable opinion prior to implementation, except when the modification is needed to eliminate an immediate hazard(s) to patients. The IRB may provide, if applicable regulatory authority(ies) permits, expedited review and approval/favorable opinion for minor change(s) in ongoing studies that have the approval/favorable opinion of the IRB. The Sponsor will submit all protocol modifications to the regulatory authority(ies) in accordance with the governing regulations.

When immediate deviation from the protocol is required to eliminate an immediate hazard(s) to patients, the Investigator will contact the Sponsor, if circumstances permit, to discuss the planned course of action. Any departures from the protocol must be fully documented in the eCRF and source documentation and reported to the appropriate study monitor or staff in a timely fashion.

---

### **13 COMPENSATION, INSURANCE AND INDEMNITY**

The Sponsor has retained an insurance policy covering, in its terms and provisions, its legal liability for injuries caused to participating persons and arising out of this research performed strictly in accordance with the scientific protocol as well as with applicable law and professional standards. The patient will be appropriately treated or compensated, or both, for any health or other problems arising from participation in this study.

---

[figure not shown]
## **14 PUBLICATION POLICY**

All information provided regarding the study, as well as all information collected/documented during the course of the study, will be regarded as confidential. The Investigator agrees not to disclose such information in any way without prior written permission from the Sponsor.

[figure not shown]
Any publication of the results, either in part or in total, including articles in journals or newspapers, oral presentations, or abstracts, by the Investigator(s) or their representative(s), shall require prior approval, notification, and review within a reasonable time frame by the Sponsor and cannot be made in violation of the Sponsor's confidentiality restrictions or to the detriment of the Sponsor's intellectual property rights.

It is anticipated that the results of this study will be presented at scientific meetings and/or published in a peer reviewed scientific or medical journal. A Publications Committee, comprising the Investigators participating in the study and representatives from the Sponsor, as appropriate, will be formed to oversee the publication of the study results, which will reflect the experience of all participating study centers. Subsequently, individual Investigators may publish results from the study in compliance with their agreement with the Sponsor. A pre-publication manuscript is to be provided to the Sponsor at least 60 days prior to the submission of the manuscript to a publisher. Similarly, the Sponsor will provide any company prepared manuscript to the Investigators for review at least 30 days prior to submission to a publisher.

---

## **Appendix A: Telephone Script, Days 2 through 14**

### Greeting

Question about general health and adverse events experienced by the patient.

“Have you had any changes in your health since our last phone call? If so, please describe.”

“If you have a personal doctor, have you been in contact with your doctor about these changes in your health, and what did your doctor recommend to you?”

Question about symptoms *[only for patients who are unable to complete the eDiary]*:

“Have you had any of the following symptoms? If so, were they mild, moderate, or severe?”

- Fatigue
- Chills
- Headache
- Cough (with or without sputum production)
- Myalgia
- Sore throat
- Shortness of breath
- Nasal congestion
- Diarrhea
- Nausea or vomiting

For each of these symptoms, the patient will be asked to grade them by the following scale:

- Not at all
- A little bit
- Somewhat
- Quite a bit
- Very much

Question about concomitant medications:

---

- “Have you taken any medications, including any new medications, changed the dose of any medications, or stopped any medications since our last phone call?”

Question about the need for a clinic or hospital visit:

- Do you feel that you will need to make a visit to see us, your personal doctor, or the hospital? If so, I will call your doctor or the hospital and let them know you will be arriving soon [or time provided by patient].”
- If the Investigator (or delegate) feels that the patient should have a clinic or hospital visit, he/she will make that recommendation.

If the patient cannot be reached, the designated family member or caregiver will be contacted for a determination of the patient’s status. The patient’s doctor may also be contacted for additional information identified during the telephone call.

---

## **Appendix B: Telephone Script, Day 21 and Day 28**

Greeting

Question on current health:

- “I am calling to check on the status of your health since you completed the first 14 days in the study. Were you admitted to the hospital at any time? If so, please provide the details of the hospital and dates.”
- Have you had any changes to your health that have required a doctor’s visit?

If the answer to either of these questions is yes, the doctor or hospital will be contacted for further details.

If the patient cannot be reached, the designated family member or caregiver will be contacted for this information.

---

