Study drug will be administered as a single intranasal dose of 0.5 mL (0.25 mL each nostril) in the supine position after which patients must remain in the supine position for 30 minutes. Patients will be observed for at least 2 hours post intranasal administration. Patients who are randomized will be considered enrolled in the study.

No in-person visits are expected during the study after Day 1 unless a participant experiences a change in symptoms or AE that requires a visit for assessment.

---

Prior to discharge from the study center on Day 1, patients will be provided with:

- A fingertip pulse oximetry device connecting to a tablet that will be supplied to the patient to measure resting SpO2 and resting pulse rate remotely. Patients will be trained on the use of the device and tablet
- A digital thermometer for measurement of oral temperature
- Instructions regarding how to take the above measurements and access and complete a web-based electronic diary (eDiary)

After discharge on Day 1, patients will return home for the duration of the study. Patients are to measure resting SpO2, resting pulse rate and oral temperature twice daily at 09:00 hours and 16:00 hours, with a 1-hour window around each time point, and at any time they experience worsening symptoms until Day 14 or hospitalization, whichever comes first. Patients are to record COVID-19-related symptoms daily during this same time period. Study center personnel will contact patients daily by telephone during this period to document the patient's clinical status, record concomitant medications and monitor for AEs.

After Day 14, study center personnel will contact patients via telephone approximately every 7±2 days for 14 additional days to determine if they were hospitalized and to follow AEs that were not resolved by Day 14. If the patient is hospitalized at any time, the dates and times of hospital admission/discharge, ICU admission/discharge, and ventilation requirement are to be recorded, as applicable. Patients who remain hospitalized at the end of 28 days will be followed through Day 42 or death, whichever is sooner. If a patient is discharged and then readmitted before Day 42, he/she will be followed until Day 42.

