**Table 1 Schedule of Events – Screening and Treatment Periods**

Procedure	Study Visit Type / Day			
	Screening	Study Drug Treatment	Diary Completion/ Telephone Contact	Telephone Contact
	Study Center Visit		Remote Visit	
	Day 1 Pre-Dose	Day 1	Daily Days 1 to 14	Days 21 and 28 ±2 days
Informed consent	X			
Eligibility criteria check	X			
Demographics	X			
Medical history	X			
Focused cardiovascular and respiratory physical examination	X			
Height and weight	X			
Blood pressure and respiratory rate	X			
Urine pregnancy test a	X			
Randomization	X			
Study drug administration b		X		
Resting SpO 2 c	X		X d	
Resting pulse rate c	X		X d	
Oral temperature c	X		X d	
Baseline/Concomitant medications	X		X	X
AEs			X	X
eDiary completion for COVID-19 symptoms e	X		X	
Criteria for the Assessment of Severity of Illness in Patients with COVID-19 f	X			X
Daily telephone contact to document concomitant medications, clinical and hospitalization status and AEs g			X	
Follow-up contact for hospitalization status, COVID-19 outcomes, and AEs h				X

a For women of child-bearing potential only. Results must be available and confirmed to be negative before study drug administration.

b Study drug is to be administered with the patient in the supine position. The patient is to remain in the supine position for 30 minutes thereafter and be observed for at least 2 hours post intranasal administration.

c To be measured remotely daily at 09:00 and 16:00 hours or at any time the patient experiences worsening symptoms using the study-supplied devices and recorded in the eDiary. Resting SpO2 and pulse are to be measured at rest for 2 minutes. A ±1 hour window will be allowed. On Day 1, only the afternoon (16:00 hours) measurement is required and may be measured at the study center or remotely.

d If the Screening visit occurs in the morning, the patient will be responsible for recording the 16:00 measurements at home later that day; if the visit occurs after 16:00, measurements will commence at home the following morning.

- e The following symptoms will be recorded: fatigue, chills, headache, cough (with or without sputum production), myalgia, sore throat, shortness of breath, nasal congestion, diarrhea, and nausea or vomiting.

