  - f After Screening, the patient will be assessed at different timepoints over the course of the trial. The final determination will be made on Day 28 in patients who are not hospitalized and Day 42 in patients who are hospitalized.
  - g Telephone calls to the patient will commence on Day 2. The script for these calls is provided in [Appendix A](#).
  - h The script for the Day 21 and Day 28 phone calls is provided in [Appendix B](#). For hospitalized patients, the dates and times of hospital admission/discharge, date and time of intensive care unit admission/discharge, and ventilation requirement are to be recorded, as applicable. Patients who remain hospitalized at the end of 28 days will be followed through Day 42 or death, whichever is sooner.
-

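### The Day 21 and Day 28 telephone script does not prompt for unresolved AEs, medications or symptoms that Table 1 schedules at those calls

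*Protocol*

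**What the plan says.** Protocol Table 1 has a telephone column headed "Days 21 and 28 ±2 days". Four rows are marked in it: concomitant medications, AEs, the Appendix C severity criteria, and a row labelled "Follow-up contact for hospitalization status, COVID-19 outcomes, and AEs". SAP Table 2 repeats this. Footnote h ties the column to one instrument: "The script for the Day 21 and Day 28 phone calls is provided in" Appendix B.

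Section 4.1 gives two purposes for the calls after Day 14: to learn of hospitalizations and "to follow AEs that were not resolved by Day 14". Section 8.3.4 makes telephone the route for that follow-up. On severity, Table 1 footnote f says: "The final determination will be made on Day 28 in patients who are not hospitalized and Day 42 in patients who are hospitalized". Section 8.2.4 says the same. Section 6.7 requires medications, including supplemental oxygen, to be documented for 30 days after dosing.

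Appendix B contains two questions. The first is "Were you admitted to the hospital at any time", with a request for details. The second begins "Have you had any changes to your health that have required a doctor" and is limited to changes that led to a doctor's visit. The next step depends on the answers: "If the answer to either of these questions is yes, the doctor or hospital will be contacted for further details". A family member or caregiver is contacted when staff are unable to reach the patient.

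**The concern.** The script is narrower than the schedule it serves. A patient who is at home, has not been admitted and has not seen a doctor answers no twice, and the script then ends without asking about anything else in the column.

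Three kinds of data are exposed:

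- the resolution and end date of an AE that was open at Day 14;
- medication use between Day 14 and Day 28, including antipyretics and bronchodilators (a safety endpoint in Section 3.3, collected through concomitant medications under Section 8.3.5);
- the symptoms on which the Day 28 severity class rests.

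Information not asked for at the time is hard to recover later. In the tables it can look like an absence of events or of medication use. SAP Section 9.10.1 plans an AE summary from Day 1 to Day 42, so the thinly collected period would be reported together with the closely monitored first 14 days.

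**Working it through.** No calculation applies. The plan states no figure on this point, and Protocol Section 10.1 gives no power, effect size or event rate. The check sets each scheduled item against both scripts and against any other scheduled source after Day 14.

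| Scheduled at Days 21 and 28 | Appendix A (Days 2 to 14) | Appendix B (Days 21 and 28) | Other scheduled source after Day 14, patient at home |
|---|---|---|---|
| Hospitalization status | Asks about need for a hospital visit | Asked directly | Not needed |
| AEs, including those open at Day 14 | Asks about any change in health | Only if a doctor was seen or the patient was admitted; no question on resolution or end date | None, but Sections 8.3.4 and 9.2 still require follow-up |
| Concomitant medications and oxygen | Medication question; none specific to oxygen | Not asked | None |
| Severity criteria: symptoms | Symptom list, for patients who cannot complete the eDiary | Not asked | None; the eDiary ends at Day 14 (Section 8.2.2) |
| Severity criteria: respiratory rate, heart rate, oxygen need | Not asked | Not asked | None; scheduled SpO2 and pulse readings end after 14 days (Section 8.2.1.2), and respiratory rate is scheduled only at Screening |

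**AEs.** The question in Appendix A carries no condition. The one in Appendix B requires a doctor's visit, and Section 8 says patients need not have a personal doctor, so the question is weakest for those patients.

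**Severity.** In Appendix C the no-symptom and mild classes are separated by symptoms. The moderate class adds exertional breathlessness and clinical signs. A patient who answers no twice could be asymptomatic, mild or possibly moderate. AE pages would not settle this, because Section 9.1.1 keeps worsening of the COVID-19 symptoms present at Screening out of AE reporting.

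**Recording windows.** The documents disagree on what is due after Day 14:

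| Place | AEs | Medications |
|---|---|---|
| Table 1 | Marked at Days 21 and 28 | Marked at Days 21 and 28 |
| Protocol 6.7 | Not addressed | Through 30 days after dosing |
| Protocol 8.3.4 | New AEs to Day 14 or hospitalization; then telephone follow-up until resolved, stabilized or handed over | Not addressed |
| Protocol 9.2 | Recorded to Day 14 or hospitalization; monitored until resolved or stabilized | Recorded to Day 14 or hospitalization |
| SAP 9.10.1 | Summarized from Day 1 to Day 42 | Not addressed |

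Under every one of these windows, an AE open at Day 14 in a patient at home still needs follow-up, and Appendix B does not prompt for it. Whether medications are due after Day 14 depends on which window governs.

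**The case against.** The strongest reply is that a script is a minimum and not a limit. Section 4.1 states the purpose of the calls, Sections 8.3.4 and 9.2 require AEs to be followed until resolved or stabilized, and Section 9.2 gives an open health question as an example. Table 1 itself tells sites to collect these items, and nothing forbids unscripted questions. This stands. A reader might infer that the scheduled items cannot be completed, and the documents do not support that. They support saying that the script does not prompt for them. With up to 12 centers, relying on unscripted questions still invites uneven collection.

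A reader might also infer that the script is the only source for patients at home. That goes too far. A yes answer sends staff to the doctor or hospital, Section 8.4 provides for unscheduled visits, and Section 8.2.1 leaves the oximeter with the patient for the duration of the study. None of these, however, is a scheduled source for a patient who answers no twice.

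On medications, Section 9.2 ends recording at Day 14, and on that reading no later question is needed. This also stands, as one side of a contradiction with Section 6.7 and Table 1.

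On severity, the Appendix C class is not among the primary, secondary or safety endpoints, and SAP Section 9 sets out no analysis of it. This is correct and limits the consequence.

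**Conclusion.** The point holds as a mismatch between the schedule and the instrument, and it is minor. Of the four rows marked at Days 21 and 28, medications and the severity criteria are not elicited by the script, and AEs are elicited only in part. The follow-up row is met for hospitalization status but not for AEs that involved neither an admission nor a doctor's visit.

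What is at risk is AE outcomes after Day 14, medication use after Day 14 (if Section 6.7 and Table 1 govern), and the symptom basis of the Day 28 severity class in patients at home. The hospitalization component of the primary endpoint is asked about and is unaffected. Hospitalized patients are less exposed, because Section 8.2.5 expects most of their data to come from the medical record.

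A reader might try to count the patients affected by assuming a hospitalization rate. The documents give no expected rate, and the percentages in Section 7.2 are thresholds for a halt. Such a count would also treat anyone ever admitted as still in hospital at Day 28, and would ignore patients for whom a yes answer brings in outside records. No count is offered.

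The conclusion assumes that sites work from Appendix B as written. The more they add questions of their own, the smaller the loss and the less uniform the data.

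**What to change.** 1. Add to Appendix B the Appendix A questions on changes in health, medications and the symptom list with its five-level scale. Ask the symptom list of all patients, since the eDiary has ended. Make the health-change question independent of a doctor's visit.
2. Add a line for each AE open at Day 14 (current status and end date) and one question on oxygen use at home.
3. Reconcile the recording windows: Section 6.7 and Table 1 against Sections 8.3.4 and 9.2, and all of these against the Day 1 to Day 42 summary in SAP Section 9.10.1.
4. The added questions do not supply respiratory or heart rate. State where these come from at Day 28, or remove the severity item from the Day 21 and 28 column for patients at home.

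Most of the wording already exists in Appendix A. The cost is a script edit, a consistency edit to the sections named, and slightly longer calls on two contacts already scheduled.
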